#### 2. STUDY DESIGN

#### 2.1. OVERALL DESIGN

This study is a multi centre, prospective two-way randomized comparative study, involving 100 patients, recruited among up to 2 centers (approximately 50 patients from each site). Patients will be randomized at the time of surgery into two groups, as detailed below.

#### 2.2. STUDY GROUPS/TREATMENTS

The first group will receive a Taperloc Complete Reduced Distal standard length stem, and the second group will receive a Taperloc Complete Reduced Distal Microplasty stem.

### 2.3. NUMBER OF SITES AND SUBJECTS/PROCEDURES

The total sample size is 100 hips in 100 patients recruited from up to two sites.

### 2.4. EFFICACY AND/OR SAFETY HYPOTHESES

There will be no difference of BMD change between both groups.

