#### 1. INTRODUCTION

#### 1.1. BACKGROUND

The Taperloc Microplasty cementless stem is designed to transmit load to the proximal femur, thereby preserving bone density, and preventing long term instability and loosening secondary to proximal bone resorption. The primary aim of this study is therefore to compare the postoperative changes in bone density with the Taperloc Microplasty stem, using the standard length Taperloc stem as a control.

In addition, the Taperloc stem has historically had a neck angle of 138°. There have been criticisms that this neck angle is too high for the typical Korean population. The newer Taperloc Complete system (both Microplasty and standard length) has a neck angle of 133°. A secondary aim is occurrence ratio of thigh pain difference between Microplasty and standard stem in Korean population

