### 1.3. RATIONALE FOR CURRENT STUDY

Stress shielding in cementless hip replacement leads to bone resorption. Not only does that increase the likelihood of long term aseptic loosening, but the reduction in bone stock could compromise the outcome of revision surgery. This is particularly important considering that cementless components are frequently used preferentially in young patients. Not only is the revision risk for a given implantation time higher with young patients, but life expectancy is higher as well. This means that young patients are much more likely to need revision surgery in their lifetime. Preservation of bone stock in order to keep revision options open is therefore a very important consideration.

One way to preserve the bone stock and to reduce stress-shielding bone resorption of the proximal femur is by removing the distal stem of the femoral component and providing metaphyseal fixation. Alternatively, reducing the size of the distal stem could also encourage metaphyseal fixation. The questions arise which is most effective at encouraging proximal load

transfer, and whether it is possible to obtain strong and long-lasting fixation of the femoral component without diaphyseal anchoring.

The rationale for this study is therefore to determine whether radiographic results and stress shielding are similar between the short and conventional length cementless femoral components with identical metaphyseal design.

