#### 1.4. STUDY PURPOSES

The main objectives of the study are to:

- Compare the postoperative changes in bone density with the Taperloc Microplasty stem, using the standard length Taperloc stem as a control.
- Compare and confirm the stability and fixation of short and standard Taperloc hip implants.
- Compare clinical scores in patients receiving the short and standard Taperloc stems.
- Collect survivorship data
- Determine whether the geometry and options available with the Taperloc Complete hip system can accurately reconstruct leg length and offset in this patient population.

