#### **Exploratory Analyses**

Exploratory Analyses described below will be carried out if possible, depending on the data. If empty cells exist or models do not converge, these analyses will not be performed.

Repeated measures ANOVA models will be developed for each of the Gruen Zones to determine the effect of visit (time), treatment and baseline value of BMD on the BMD results. Baseline factors may also be included. To determine whether a factor has an effect on the BMD results, a Type 3 analysis of effects based on the F test will be conducted. Hypothesis testing will use  $\alpha$  = 0.05.

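### The only BMD-specific analysis is an exploratory F test of difference with no estimate, interval or margin, so it cannot answer the Section 1.3 question of similarity, and a non-significant result could not be interpreted

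*Combined protocol and SAP*

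**What the plan says.** BMD change around the implant is one of two primary endpoints (Section 2.5). The text on the BMD question is as follows.

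- **Section 2.4**, the only hypothesis: "There will be no difference of BMD change between both groups". It gives no alternative, direction or margin.
- **Section 1.3**, rationale: the study is to "determine whether radiographic results and stress shielding are similar between the short and conventional length cementless femoral components".
- **Section 1.4**, first objective: "Compare the postoperative changes in bone density with the Taperloc Microplasty stem, using the standard length Taperloc stem as a control".
- **Section 6.2, Exploratory Analyses**: repeated-measures models for each Gruen zone are to be developed "to determine the effect of visit (time), treatment and baseline value of BMD on the BMD results". The decision tool, at alpha 0.05, is stated thus, for judging "whether a factor has an effect on the BMD results, a Type 3 analysis of effects based on the F test will be conducted". The block is conditional: "Exploratory Analyses described below will be carried out if possible, depending on the data".

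Elsewhere in Section 6.2, a 0.05 error rate is set for the primary analysis without naming a test. The paragraph on continuous measures covers baseline and secondary outcomes only. Section 6.1 sizes the trial on thigh pain. Section 2.6.1 schedules DEXA immediately after surgery and at 1, 2 and 5 years.

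**The concern.** The rationale asks a similarity question and the hypothesis is worded as no difference, but the planned tool is a significance test for a difference. If similarity is the aim, that test cannot show it: rejecting gives evidence of a difference, and failing to reject gives no evidence of its absence. If Section 2.4 is an ordinary null, the test suits the question, but a non-significant result leaves the reader without the quantity needed to interpret it, namely how large a difference in bone loss the data still allow. With no BMD effect size, standard deviation or power stated, nothing else in the plan fills that gap. At stake is whether a null result on a primary endpoint can be interpreted at all.

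**Working it through.** **1. Is there a BMD figure to reproduce?** No. The documents give no BMD standard deviation, target difference, margin or power. The figure of about 40 per group in Section 6.1 concerns thigh pain; it serves below only as a smaller arm size.

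**2. Does any other provision supply an estimate or interval?** No. The continuous-measures paragraph in Section 6.2 does not extend to primary outcomes. If it were applied to BMD anyway, its examples (t-test, Wilcoxon test, one-way ANOVA) are again tests of difference. No interval or margin rule appears in any section.

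**3. How informative is a non-significant result?** Inputs: 50 per arm (Study Summary) and, for comparison, 40 per arm (Section 6.1). Assumptions: one zone, one visit, unadjusted, equal variances, no dropout, differences in units of the SD of BMD change.

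- Standard error = √(2/n): √(2/50) = 0.200 SD; √(2/40) = 0.224 SD.
- 95% half-width = t × SE: 1.984 × 0.200 = 0.397 SD; 1.991 × 0.224 = 0.445 SD.
- Probability of non-significance = P(|T| < t), with T noncentral t, df = 2n − 2 and noncentrality δ/SE. At n = 50 the noncentralities are 0.3/0.2 = 1.5, 0.4/0.2 = 2.0 and 0.5/0.2 = 2.5.

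| True difference | n = 50 | n = 40 |
|---|---|---|
| 0.3 SD | 68% | 74% |
| 0.4 SD | 49% | 58% |
| 0.5 SD | 30% | 40% |

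For example, an observed difference of 0.20 SD with 50 per arm is non-significant, and its interval is 0.20 ± 0.397, or −0.20 to 0.60 SD. The p-value alone does not show this.

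**4. Does baseline adjustment change the picture?** Only in part. With correlation ρ between baseline and change, the residual SD is √(1 − ρ²) and df = 2n − 3. At n = 50:

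- ρ = 0.3: residual SD 0.954, half-width 0.38 SD; non-significant in 66%, 45% and 26%.
- ρ = 0.5: residual SD 0.866, half-width 0.34 SD; non-significant in 60%, 37% and 18%.

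**5. What would a real similarity claim need?** Two one-sided tests at 5% (equivalently, a 90% interval wholly inside the margin), true difference zero, same assumptions as step 3:

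| Margin | Power at 50 per arm | n per arm for 80% power |
|---|---|---|
| 0.4 SD | 27% | 108 |
| 0.5 SD | 60% | 70 |
| 0.6 SD | 82% | 49 |

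**The case against.** The strongest reply is that Section 2.4 is simply how a null hypothesis is written, that the objective in Section 1.4 fits a two-sided comparison, and that the warning about non-significant tests applies to any trial. Much of this stands. Section 2.4 does read most naturally as a null. The Section 1.1 remark that the short stem is "designed to transmit load to the proximal femur, thereby preserving bone density" describes the device. The Section 1.3 sentence beginning "The questions arise which is most effective at encouraging proximal load" follows a discussion of two design strategies and is background. Neither is a rival hypothesis. What remains is the similarity wording in Section 1.3, which is the study's own stated rationale and which no planned analysis can address.

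Three stronger readings are tempting and are not supported:

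- **That the sponsor will report p > 0.05 as similarity.** No section says so. The point is only that nothing rules it out and no planned output would expose it.
- **That the model excludes treatment-by-visit and averages the effect over 1, 2 and 5 years.** Section 6.2 names effects of interest, not a full model formula, and does not say which visits enter. The term is unlisted, not excluded. How often a late difference would be missed depends on profiles, correlations and dropout that a reviewer would have to invent, so no such figure is used here.
- **That the trial must become an equivalence study.** A two-sided comparison is legitimate if it is stated and reported as one.

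It is also fair to say that the fix does not give BMD a designated primary analysis, zone or time point. That is a separate matter.

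**Conclusion.** The concern holds in a limited form. As written, the BMD analysis cannot answer the similarity question in Section 1.3, and a non-significant F test would leave the Section 2.4 hypothesis neither supported nor usefully bounded. In the illustration, differences of 0.3 to 0.5 SD would go undetected in 68% to 30% of trials with 50 per arm, and the 95% interval would be about ±0.40 SD. These figures rest on an assumed SD scale, one zone, one visit, no adjustment and no dropout. They show that imprecision is a live explanation for a null result, not how likely one is. The miss rate falls as the true difference grows. The data collected are unaffected, and the remedy is cheap. The change should be made, but the point does not invalidate the trial.

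**What to change.** 1. **Section 2.4.** Label the sentence as a two-sided H0 on mean BMD change from the immediate post-operative DEXA, and add H1: the mean change differs between groups.
2. **Section 6.2.** Include treatment-by-visit in the BMD model. For each Gruen zone, report the baseline-adjusted between-group difference in BMD change at 1, 2 and 5 years with its 95% confidence interval. If the model does not converge, obtain the same differences from a baseline-adjusted comparison at each visit.
3. **Sections 6.2 and 1.3.** State that p > 0.05 will not be reported as no difference or as similarity, and that any similarity claim needs a margin fixed and justified before analysis, with the 90% interval wholly inside it. Bring the similarity wording in Section 1.3 into line with Section 2.4.

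**Cost.** Text and one model term; no new patients, visits or scans. There are three downsides:

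- The trial gives up concluding no difference from a non-significant test.
- Visit-specific intervals are wider than a visit-averaged one when the difference is constant. With 50 per arm, ρ = 0.3 and between-visit correlation r, the averaged residual variance is (1 + 2r)/3 − 0.09. For r from 0.5 to 0.9 the averaged half-width is 1.985 × 0.2 × √0.577 = 0.30 to 1.985 × 0.2 × √0.843 = 0.36 SD, against 0.38 SD at one visit.
- Many unadjusted intervals are shown. With an assumed 3 to 7 zones at three visits there are 9 to 21, of which 5% on average would exclude zero by chance, so they are descriptive.

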### 2.5. PRIMARY AND SECONDARY ENDPOINTS

# Primary Endpoints:

- Change in bone mineral density around the implant
- Incidence of thigh pain

## Secondary Endpoints:

- Postoperative restoration of femoral offset and leg length
- Radiographic measurements of stability and fixation
- Overall Survivorship
- Harris Hip Score
- Complications

#### 2.6. ASSESSMENT PROCEDURE

### 2.6.1. ASSESSMENT TIMELINES/SCHEDULE

	Pre-op	Intraop	Immediate Post-op	6 weeks	6 months	1 year	2 years	5 years
Operative Form		Х						
Standard Radiographs	Х			Х		Х	Х	Х
DEXA			Х			Х	Х	Х
Modified Harris Hip Score	Х				Х	Х	Х	Х
Thigh pain	Х			Х	Х	Х	Х	Х
Complications		Any Time						

#### 2.6.2. ALLOWED WINDOW OF EACH SCHEDULE

Follow-up Time Point	Allowed Window		
Immediate Post-Op	+ 1 Week		
6 weeks	1-2 Months		
6 months	+/- 1 Month		
1 Year	+/- 2 Months		
2 Year	+/- 3 Months		
5 Year	+/- 6 Months		

#### 2.7. STUDY DURATION

The estimated study duration is 6 years with 1 year allotted for site and patient enrollment and 5 years of active follow-up.

### 3. SELECTION AND WITHDRAWAL OF SUBJECTS

Inclusion/exclusion criteria are identical to those indications and contraindications stated in the package insert of Taperloc hip Implants.

### 3.1. INCLUSION CRITERIA

Patients suitable for primary Total Hip Replacement

Patients with degenerative joint disease (inflammatory or non-inflammatory) or any of the composite diagnoses of:

- a. Osteoarthritis
- b. Avascular necrosis
- c. Legg Perthes
- d. Rheumatoid arthritis
- e. Diastrophic variant
- f. Fused hip
- g. Sequelae of slipped capital epiphysis
- h. Traumatic arthritis
- i. Patients aged over 20

j. Patients must be able to understand instructions and be willing to return for follow-up

#### 3.2. EXCLUSION CRITERIA

Absolute contraindications include: infection, sepsis, and osteomyelitis.

Relative contraindications include:

- Uncooperative patient or patient with neurologic disorders who are incapable of following directions
- b. Small femoral canal
- c. Severe osteoporosis (patients over 65 years old)
- d. Metabolic disorders which may impair bone formation
- e. Osteomalacia
- f. Distant foci of infections which may spread to the implant site
- g. Rapid joint destruction, marked bone loss or bone resorption apparent on roentgenogram
- h. Vascular insufficiency, muscular atrophy, or neuromuscular disease
- i. Pregnancy
- j. Fracture of the pelvis
- k. Subcapital fractures

#### 4. PROTOCOL DEVIATION MANAGEMENT AND REPORTING

Any deviation from the protocol should be documented on the "Protocol Deviation" CEF. Protocol Deviations should be reported to the study Sponsor within ten days of knowledge of the reported event.

#### 5. ADVERSE EVENT MANAGEMENT AND REPORTING

Any adverse event, according to definitions section 18, should be documented on the "Complication" CRF. A record of all adverse events, including details of the nature, onset, duration, severity, relationship to the device, relationship to the operative procedure and outcome, will be made on the relevant section(s) of the subject's CRF.

Complications should be reported to the study Sponsor within ten days of knowledge of the reported event. If the event is considered an unanticipated adverse event, it should be reported to the study Sponsor within 5 days of knowledge of the reported event.

#### 6. DATA ANALYSES

#### 6.1. SAMPLE SIZE JUSTIFICATION

We performed a sample size calculation based on detecting a difference in the incidence of postoperative thigh pain between the 2 study groups, assuming an overall  $\alpha$  error (2 sided) of 5% with a statistical power of 80% ( $\beta$  error = .20). We assumed that the incidence of thigh pain in the conventional femoral implant group would be 15% compared to 5% in the short anatomical femoral implant group at 2-year follow-up. With these assumptions, approximately 40 patients per study group were needed.

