### 6.2. DESCRIPTION OF STATISTICAL ANALYSES

### Significance Levels

The Type I error rate for the primary study analysis will be 0.05.

Comparisons for secondary, exploratory, and safety analyses will use  $\alpha$  = 0.05, with no adjustment for multiple comparisons.

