#### **Categorical Data Analyses**

Comparisons of study groups with regard to categorical baseline, secondary and safety outcomes will be performed using standard statistical tests and will be chosen as appropriate for the scale and distribution of the measures being analyzed.

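### Section 6.1's 40 patients per group does not follow from its own inputs: 15% versus 5% thigh pain needs about 140 per group, and the planned 50 gives under 40% power

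*Combined protocol and SAP*

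**What the plan says.** Section 6.1 states every input to its calculation. The endpoint is the incidence of postoperative thigh pain at 2 years, with a two-sided 5% error rate and 80% power. It assumes that "the incidence of thigh pain in the conventional femoral implant group would be 15% compared to 5" per cent in the short-stem group, and concludes: "With these assumptions, approximately 40 patients per study group were needed".

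Section 2.5 lists "Incidence of thigh pain" as one of two primary endpoints, beside change in bone mineral density (BMD). The Study Summary does the same and gives the arm split as 50 and 50. Section 2.3 confirms the total: "The total sample size is 100 hips in 100 patients recruited from up to two sites".

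Section 6.2 adds: "The Type I error rate for the primary study analysis will be 0.05". Its paragraph on categorical data reads: "Comparisons of study groups with regard to categorical baseline, secondary and safety outcomes will be performed using standard statistical tests". It names no test and does not mention primary outcomes. No loss to follow-up rate and no sample size calculation for BMD appear anywhere.

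**The concern.** A fall from 15% to 5% is a 10-point difference between two small proportions. Detecting it with 80% power normally takes well over 100 patients per group, so 40 looks too small by a wide margin.

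Thigh pain is the only endpoint for which the trial's size is justified. If the calculation is wrong, nothing in the document supports 100 patients, and readers are told of a power that the design lacks. If the assumed benefit is real, the trial would then miss it more often than not. A non-significant result could easily be taken as showing that the stems are alike, since Section 1.3 asks whether radiographic results and stress shielding are similar.

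**Working it through.** **Inputs.** From Section 6.1: p1 = 0.15, p2 = 0.05, difference d = 0.10, two-sided alpha 0.05 (z = 1.960), power 0.80 (z = 0.842). From the Study Summary: 50 per group. The mean proportion is 0.10. The variance terms are 2 × 0.10 × 0.90 = 0.180 (pooled) and 0.15 × 0.85 + 0.05 × 0.95 = 0.175 (unpooled).

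**Trying to reproduce 40 per group.**

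- Pooled variance: n = (1.960 × √0.180 + 0.842 × √0.175)² / d² = (0.8315 + 0.3521)² / 0.01 = 140.1, so **141**.
- Unpooled variance: n = (1.960 + 0.842)² × 0.175 / 0.01 = 137.4, so **138**.
- Arcsine: n = 2 × (1.960 + 0.842)² / (2·asin√0.15 − 2·asin√0.05)² = 132.4, so **133**.
- Continuity-corrected, from the pooled n: (140.1 / 4) × (1 + √(1 + 4 / (140.1 × 0.10)))² = 159.5, so **160**.
- One-sided 5%, which contradicts the stated two-sided test: 111 pooled, and 105 to 130 across the same four methods.

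None is near 40. The ratios are 141 / 40 = 3.5 and 141 / 50 = 2.8. With 5% in the short-stem group, 40 per group fits a conventional-stem rate of about 28%, not 15%.

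**Power for 15% versus 5%, two-sided 5%.** The normal approximation is Φ[(d√n − 1.960 × √0.180) / √0.175]. At n = 50 this is Φ[(0.7071 − 0.8315) / 0.4183] = Φ(−0.297) = 0.383. The exact figures enumerate all pairs of binomial outcomes.

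| Evaluable per group | Normal approximation | Chi-square, uncorrected (exact) | Fisher (exact) |
|---|---|---|---|
| 40 | 32% | 35% | 18% |
| 45 | 35% | 39% | 23% |
| 50 | 38% | 39% | 24% |

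The row for 45 represents 10% loss by 2 years. That rate is an assumption, because the plan gives none.

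**What the design could detect.** At 50 per group and 5% in the short-stem group, 80% power is reached at a conventional-stem rate of about 23% (exact chi-square), 25% (normal approximation) or 26% (Fisher; the crossing is at 26.4%).

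**What the assumed result would look like.** At 40 per group the assumed rates are exactly 6 and 2 patients. Chi-square gives p = 0.14 and Fisher p = 0.26. At 50 per group the expected counts are 7.5 and 2.5; the four nearest tables (7 or 8 versus 2 or 3) give p from 0.046 to 0.18 by chi-square and from 0.09 to 0.32 by Fisher.

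**Precision.** The 95% half-width for the difference is 1.96 × √(0.175 / n): 11.6 points at 50 per group and 13.0 at 40, against an assumed effect of 10 points.

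**The case against.** The strongest reply is that this is mainly a BMD trial. The Study Summary and Section 1.1 make BMD the primary purpose, Section 1.1 calls the thigh-pain comparison a secondary aim, and the one hypothesis, in Section 2.4, concerns BMD. This limits the finding: it says nothing about power for BMD. It does not remove it, because Section 2.5 and the Study Summary list thigh pain as primary and Section 6.1 rests the trial's size on it alone.

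A second reply is that the trial enrols 50 per group, not 40. Going from 40 to 50 would fit a 20% allowance for loss (40 / 0.80 = 50), although the plan states none. That could explain the step from 40 to 50, but not the gap between 40 and about 140.

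Third, the 39% for the exact chi-square test is only just under 40%. That is true, and it assumes that all 50 per group are evaluable at 2 years.

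Finally, the unnamed test is a separate gap. That is fair: no usual two-group test brings the requirement near 40, so the arithmetic error does not depend on it. Nor does the plan say that a non-significant thigh-pain result will be read as no difference. That risk is anticipated, not written in.

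**Conclusion.** The concern holds. Under the printed assumptions the requirement is 133 to 160 per group depending on the formula, not about 40. At the planned 50 per group, power is about half the stated 80% by chi-square and less than a third of it by Fisher's test, before any loss to follow-up. The wording that the figure is approximate cannot cover a 3.5-fold gap.

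The sample sizes rest only on Section 6.1's own rates, error rate and power, with equal groups. The power figures add a choice of test, because the plan names none, and complete 2-year follow-up. Whether the 40 or the rates were misstated cannot be settled from the documents. This must be corrected, because it is the only stated justification for the trial's size.

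**What to change.** Keep 100 patients, delete the 40-per-group sentence from Section 6.1, and put in its place wording such as:

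> With 50 evaluable patients per group at 2 years, power to detect thigh pain of 15% versus 5% at the two-sided 5% level is about 38% (chi-square, normal approximation) or 24% (Fisher's exact test). Against a rate of 5%, 80% power requires a rate in the conventional group of about 25% (normal approximation) or 26% (Fisher; 26.4%).

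If the sponsor holds a calculation that yields 40, its real inputs should be printed instead. If 80% power for 15% versus 5% is to be kept, about 140 per group are needed (about 160 with Fisher's test or a continuity correction), before any allowance for loss.

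Two additions are advisable but not needed to correct the arithmetic. Section 6.2 should name the test for thigh pain as a primary endpoint. The result should be reported as a difference with its 95% confidence interval (half-width about 12 points at 50 per group), with a statement that non-significance will not be taken as evidence of no difference.

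The cost is one paragraph plus the amendment and IRB approval required by the section on Institutional Review Boards. No extra patients are needed if the size stays at 100. The drawback is that the protocol will then openly state low power for a primary endpoint.
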